8.4.8.2 Unsolicited Adverse Events

Unsolicited AEs will be followed up for 28 days. All adverse events with Grade > 3 will be followed up throughout the study.

As detailed in Section 8.4, the investigator will assess unsolicited AEs that meet the definition of an AE or SAE with respect to seriousness, intensity/toxicity, and causality.

8.5 Treatment of Overdose

In this study, an overdose is defined as more than 1 dose of study vaccine in a 24-hour period or more than 2 doses of study vaccine throughout the study. Sponsor does not recommend specific treatment for an overdose. Decisions regarding dose interruptions or modifications will be made by the investigator in consultation with the Sponsor Clinical Director based on the clinical evaluation of the participant.

8.6 Pharmacokinetics

Pharmacokinetic parameters will not be evaluated in this study.

8.7 Pharmacodynamics

Pharmacodynamic parameters will not be evaluated in this study.

8.8 Biomarkers

Biomarkers are not evaluated in this study.

8.8.1 Planned Genetic Analysis Sample Collection

Planned genetic analysis samples will not be evaluated in this study.

8.9 Future Biomedical Research Sample Collection

The following specimens will be obtained as part of future biomedical research:

- DNA for future research
- Leftover main study serum from neutralizing antibodies by PNA stored for future research
- Leftover main study serum from total anti-spike IgG antibodies by ELISA stored for future research
- Leftover main study serum from immunological assessments stored for future research (Panels C, D, G, and H only)
- Leftover main study PBMCs from immunological assessments stored for future research

8.10 Health Economics Medical Resource Utilization and Health Economics

Health Economics OR Medical Resource Utilization and Health Economics are not evaluated in this study.

8.11 Visit Requirements

Visit requirements are outlined in Section 1.3. Specific procedure-related details are provided in Section 8.

8.11.1 Screening

Within 28 days prior to allocation/randomization, potential participants will be evaluated to determine that they fulfill the entry requirements as set forth in Section 5.

Participants may be rescreened after consultation with the Sponsor. Rescreening should include all screening procedures listed in the SoA, including consent review. Rescreen procedures cannot be conducted the day prior to intervention allocation/randomization if there are Day -1 procedures planned per protocol.

8.11.2 Vaccination Visit

Refer to the SoA (Section 1.3) and Administrative General Procedures (Section 8.1).

Day 1

Participants will be randomized and vaccinated at the study site on Day 1, as set forth in the SoA and Section 6.

If all criteria are fulfilled, no significant change in the participant's health, participants will be assigned a study randomization number to receive V591 or placebo. The assigned study intervention (V591 or placebo) will be administered via IM (left or right deltoid) injection. The time and the arm (left or right) in which the vaccine was injected will be recorded in the participant's source data and in the eCRF.

After injection, the participants will remain in the clinical sites for medical supervision and monitoring as the following:

- Panels A and B: for a minimum of 8 hours after the first and the second injection.
- Panel E: at a minimum for the first 5 subjects for a minimum of 8 hours post-injection. The rest of the participants for a minimum of 1 hour post-injection.
- All other panels: for a minimum of 1 hour post-injection.

Post vaccination safety assessments (VS and local reaction of the injection site and general reaction) on Day 1 will be performed as set forth in the SoA.

Participant will be provided with a VRC, a ruler and a thermometer and they will receive instructions on how to measure temperature and record adverse events during the subsequent 28 days after the injection. The VRC will be returned on the next visit at the clinical sites.

Subject will be given an emergency card with a phone number to call in case of questions or upon occurrence of any AE.

At the end of the visit, which lasts approximately 9 hours in Panels A, B and for the sentinel participants of panel E, and approximately 2 hours in other panels and remaining participants of panel E, once the study physician has determined that a participant is fit to be released, the participant will be discharged from the clinical site. The appointment for the phone call (24 hours \pm 6 hours) and for the next clinical visit will be scheduled and confirmed with the participant.

Day 57 (the second vaccination for 2-dose Day 1, Day 57 panels)

On Day 57 of the study, participants in the 2-dose Day 1, Day 57 panels (Panels A, B, I and J) will receive the second intramuscular injection of V591 or placebo into the deltoid muscle accordingly to protocol randomization schedule. Predose and post vaccination safety and immunogenicity assessments will be performed as set forth in the SoA. After injection, the participants will remain in the clinical sites for medical supervision and monitoring for a minimum of 8 hours after injection. (Panels A and B) and for a minimum of 1 hour after injection (Panels I and J).

Participant will be provided with a new VRC for the 28 following days. At the end of the visit, which lasts approximately 9 hours in Panels A and B , 2 hours for Panels I and J, once the study physician has determined that participant is fit to be released, the participant will be

discharged from the clinical site. The appointment for the phone call (24 hours \pm 6 hours) and for the next clinical visit will be scheduled and confirmed with the participant.

Day 169 (the second vaccination for 2-dose Day 1, Day 169 panels)

On Day 169 of the study participants in the 2-dose Day 1, Day 169 panels (Panels F, K and L) will receive the second intramuscular injection of V591 or placebo into the deltoid muscle accordingly to protocol randomization schedule. Predose and post vaccination safety and immunogenicity assessments will be performed as set forth in the SoA. After injection, the participants will remain in the clinical sites for medical supervision and monitoring for a minimum of 1 hour after injection.

Participant will be provided with a new VRC for the 28 following days. At the end of the visit, which lasts approximately 2 hours, once the study physician has determined that participant is fit to be released, the participant will be discharged from the clinical site. The appointment for the phone call (24 hours \pm 6 hours) and for the next clinical visit will be scheduled and confirmed with the participant.

8.11.3 Discontinued Participants Continuing to be Monitored in the Study

At any point if a participant discontinues from treatment but continues to be monitored in the study, study procedures specified in the SoA may be completed at the discretion of the investigator and with Sponsor agreement. The subset of study procedures completed will be communicated in a PCL.

8.11.4 Poststudy

The investigator or study coordinator must notify the Sponsor when a participant has been discontinued/withdrawn from the study. If a participant discontinues for any reason at any time during the course of the study, the participant may be asked to return to the study site (or be contacted) for a post-study visit (approximately 365 days after the last vaccination) to have the applicable procedures conducted. However, the investigator may decide to perform the post-study procedures at the time of discontinuation or as soon as possible after discontinuation. If the poststudy visit occurs less than 365 days after the last study intervention, a subsequent follow-up telephone call should be made at 365 days or after (within the protocol-specified variance) of the last study intervention to determine if any SAEs, ECIs or MAAEs have occurred since the poststudy clinic visit (as well as AEs through Day 28 if not already collected).

Amendment 04:

The sponsor has decided to terminate the study based on the immunogenicity results. All participants should be asked to return to the study site (or be contacted by phone) for a final post-study visit at least 56 days post the last vaccination to have the applicable procedures conducted. The post-study procedures as outlined Section 1.3.1, 1.3.2 and 1.3.3 (Schedule of Activities for all panels) should be followed for the final post-study visit, except for the serum sample collection for immunogenicity assessments. Serum sample for neutralizing

antibodies and serum sample for total anti-spike IgG and total anti-N IgG antibodies will not be collected.

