3 HYPOTHESES, OBJECTIVES, AND ENDPOINTS

Healthy male participants and female participants between the ages of 18-55 years (inclusive) of age in Parts 1 and 2A (younger adults) and > 55 years of age in Part 2B (older adults)

Objectives	Endpoints
Primary	
To assess the safety and tolerability of V591 compared with placebo	
Solicited injection site adverse events from Day 1 through Day 5 after any study intervention
 
Solicited systemic adverse events from Day 1 through Day 14 after any study intervention
 
Unsolicited adverse events from Day 1 through Day 28 after any study intervention
 
SAEs from Day 1 throughout the duration of study
 
Medical attended AEs (MAAEs) collected from Day 1 throughout the duration of study

Secondary	
To compare the humoral immunogenicity of V591 with placebo at Day 29 (all panels) and Day 85 (Panels A, B, I, and J) or Day 197 (Panels K and L)	
Anti-SARS-CoV-2 spike serum neutralizing antibody (nAb) responses, as measured by Pseudo-virus Neutralization Assay (PNA)
 
Anti-SARS-CoV-2 spike Immunoglobulin G (IgG) responses, as measured by ELISA

To evaluate the humoral immunogenicity of V591 at all timepoints with serum collection	
Anti-SARS-CoV-2 spike serum nAb responses, as measured by Pseudo-virus Neutralization Assay (PNA)
 
Anti-SARS-CoV-2 spike IgG responses, as measured by ELISA

Tertiary/Exploratory	
To evaluate the immune response to of V591, including cell-mediated immunity	
PBMCs stimulated with SARS-CoV-2 Spike peptides for characterization of cell mediated immunity and serum to characterize the immune response to V591

[figure not shown]
Objectives	Endpoints
To characterize SARS-CoV-2 seroconversion rates among participants	Anti-SARS-CoV-2 N-protein IgG responses, as measured by immunoassay
To document confirmed diagnoses of SARS-CoV-2 infection among study participants	Laboratory confirmed diagnosis of SARS-CoV-2 infection reported as an ECI
To document study participants' exposures to confirmed SARS-CoV-2 cases	Known exposure to a confirmed case of active SARS-CoV-2 reported as an ECI

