In Part 2B, approximately 150 healthy older participants (aged > 55 years) will be enrolled in six Panels. Two Panels of older participants, Panel G and Panel H, will be administered a single dose of either $1 \cdot 10^5$ TCID₅₀ or $1 \cdot 10^6$ TCID₅₀ of V591. Two Panels of older participants, Panel I and Panel J, will be administered two doses of either $1 \cdot 10^5$ TCID₅₀ or $1 \cdot 10^6$ TCID₅₀ of V591 56 days apart. Two Panels of older participants, Panel K and Panel L, will be administered two doses of either $1 \cdot 10^5$ TCID₅₀ or $1 \cdot 10^6$ TCID₅₀ of V591 168 days apart. Twenty-five participants will be randomized into each panel per dosing regimen to receive IM vaccination of V591 or placebo in a 4:1 ratio. Part 2B may initiate based upon siDMC recommendation as outlined below and may initiate simultaneously with Part 2A. Study participants in Panels I-L may receive their second dose of V591 based upon siDMC recommendation as outlined below. Panel G, Panel H, Panel I, and Panel J may be enrolled in parallel, while Panel K and Panel L will only commence recruiting study participants after Panel G, Panel H, Panel I, and Panel J are full enrolled.

In accordance with the FDA's "Development and Licensure of Vaccines to Prevent COVID-19, Guidance for Industry", the Sponsor will make efforts recruit a representative population for this Phase 1/2 study, particularly in the Panels of older adults as this is the only planned study in Phase 1 that will include this population. In order to facilitate the enrollment of diverse study population, particularly those that have been disproportional impacted by COVID-19 and historically underrepresented in vaccine trials, older adults in Part 2B will only be recruited in the United States.

The Sponsor's standing internal Data Monitoring Committee (siDMC) will review safety and tolerability data throughout this study, will evaluate safety data for the Safety Reviews following the first and second vaccinations in the sentinel Panels, and will be convened to evaluate available data if stopping rules are met. The siDMC is a standing, internal Sponsor committee established to monitor early phase clinical studies. Additional details are provided in Section 10.1.4.1 and in the siDMC charter.

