4.3 Beginning and End of Study Definition

The overall study begins when the first participant signs (or their legally acceptable representative) provides documented informed consent. The overall study ends when the last participant completes the last study-related contact, withdraws consent, or is lost to follow-up (ie, the participant is unable to be contacted by the investigator).

A study may be paused during review of newly available preclinical/clinical safety, PK, pharmacodynamic, efficacy, or biologic data or other items of interest, prior to a final decision on continuation or termination of the study. It may be necessary to keep the study open for gathering/reviewing of additional supportive data to optimally complete the objective(s) of the study. If necessary, the appropriate amendment(s) to the protocol and/or appropriate communication(s) will be generated. If the decision has been made to end the study following this review period, the study end will be defined as the date of the Sponsor decision, and this end of study date supersedes the definitions outlined above. The Competent Authority(ies) and IRB(s)/IEC(s) will be apprised of the maximum duration of the study beyond the last participant out and the justification for keeping the study open.

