The investigator, who is a qualified physician, will assess events that meet the definition of an AE, SAE or MAAE as well as other reportable safety events with respect to seriousness, intensity/toxicity and causality.

8.4.1 Time Period and Frequency for Collecting AE, SAE, MAAE, and Other Reportable Safety Event Information

AEs, SAEs, MAAEs, and other reportable safety events that occur after the participant provides documented informed consent form, but before intervention allocation/randomization, must be reported by the investigator for randomized participants only if the event is the result of a protocol-specified intervention, including but not limited to washout or discontinuation of usual therapy, diet, placebo, or a procedure.

From the time of vaccination all AEs must be reported by the investigator up to 28 days after any study vaccination. SAEs, MAAEs, ECIs, arthralgia of any grade and other reportable safety events must be reported by the investigator from the time of vaccination through the end of study visit.

Additionally, any SAE brought to the attention of an investigator any time outside of the time period specified in the previous paragraph also must be reported immediately to the Sponsor if the event is considered related to study intervention.

Investigators are not obligated to actively seek AEs or SAEs or other reportable safety events in former study participants. However, if the investigator learns of any SAE, including a death, at any time after a participant has been discharged from the study, and he/she considers the event to be reasonably related to the study intervention or study participation, the investigator must promptly notify the Sponsor.

All initial and follow-up AEs, SAEs, MAAEs, and other reportable safety events will be recorded and reported to the Sponsor or designee within the time frames as indicated in [Table 5](#).

Table 5 Reporting Time Periods and Time Frames for Adverse Events and Other Reportable Safety Events

Type of Event	Reporting Time Period: Consent to Randomization/ Allocation (Randomized participants only)	Reporting Time Period: Randomization/ Allocation through Protocol-specified Follow-up Period	Reporting Time Period: After the Protocol-specified Follow-up Period	Time Frame to Report Event and Follow-up Information to Sponsor:

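### After Amendment 04 the primary SAE and MAAE endpoints have a minimum follow-up but no common cut-off, so crude dose-group comparisons can differ through time at risk alone

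*Combined protocol and SAP*

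**What the plan says.** Section 3 gives two primary endpoints an open-ended window: "SAEs from Day 1 throughout the duration of study" and "Medical attended AEs (MAAEs) collected from Day 1 throughout the duration of study". Section 8.4.1 has investigators report these events "from the time of vaccination through the end of study visit".

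The Amendment 04 paragraph of Section 8.11.4 asks every participant to come back, or to be telephoned, for "a final post-study visit at least 56 days post the last vaccination to have the applicable procedures conducted". This fixes the earliest date of last contact and leaves the latest date open. The rationale for Amendment 04 adds that active follow-up stops there, that spontaneous reports of SAEs and other specified events may go on for the original periods, and that the final analysis uses data to at least Day 56.

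Twelve-month text is still current elsewhere. The Synopsis (Duration of Participation) gives 12 months of follow-up after the last vaccination, and Section 6.6 equates completing the study with 365 days after it.

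Section 9.6.1 and Table 9 put any SAE, any MAAE and any ECI in Tier 2, analysed as differences in the proportion of participants with an event, with Miettinen and Nurminen intervals. No cut-off day, person-time denominator or censoring rule is given. The SAP does not say whether placebo is pooled or matched by panel. Table 12 lists treatment by dose with one placebo row.

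**The concern.** A crude proportion can be interpreted across groups only if the groups were watched for about the same time. Here the time depends on the regimen (one dose, or two doses 56 or 168 days apart), on whether the second dose was given before termination, and on when the site held the final visit. Recruitment order may add to this: "Panel K and Panel L will only commence recruiting study participants after Panel G, Panel H, Panel I, and Panel J are full enrolled", so closing the study by calendar date could give panels different follow-up.

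The 10^7 dose exists only as a single injection in Panel E, and the 10^4/10^5 regimen only in Panel F. Pooled placebo mixes all regimens. The highest dose could therefore look safer than placebo only because it was observed for less time. In addition, events actively sought up to the final visit and events reported spontaneously afterwards could enter the same endpoint.

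**Working it through.** **1. The plan's own SAE figures (Section 9.9.1, n = 228 on V591).**
- 1 − (1 − 0.007)^228 = 79.8% (stated 80%).
- 1 − (1 − 0.003)^228 = 49.6% (stated 50%).
- Upper bound with no events: 1 − 0.025^(1/228) = 1.605% (stated <1.61%).

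All three reproduce, but none carries a time window. If 0.70% is taken as a 364-day risk (an assumption), the 56-day risk is 1 − 0.993^(56/364) = 0.108%. The chance of seeing at least one SAE is then 1 − (1 − 0.00108)^228 = 21.8%. (The plan also uses 208 for the V591 total; that mismatch is a separate matter.)

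**2. Minimum time at risk from Day 1 under Section 8.11.4.**
- One-dose panels (C, D, E, G, H): 56 days.
- Day 57 panels (A, B, I, J), both doses given: 56 + 56 = 112 days.
- Day 169 panels (F, K, L), both doses given: 168 + 56 = 224 days; without dose 2, 56 days.

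**3. Mean minimum follow-up by group, using the allocation in Tables 3 and 4, all second doses given.**
- 10^7: 56 days. 10^4/10^5: 224 days.
- 10^5, and likewise 10^6: (40×56 + 24×112 + 20×224)/84 = 112 days.
- Pooled placebo: (25×56 + 12×112 + 15×224)/52 = 117.4 days.
- Pooled V591: also 117.4 days, because each panel is 4:1.

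If Day 169 doses are not given, pooled placebo has (40×56 + 12×112)/52 = 68.9 days.

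**4. Expected crude risk with no vaccine effect.** Assume a constant hazard and a risk R over 364 days, so that risk by day t is 1 − (1 − R)^(t/364). With R = 5% this gives 0.79% at 56 days, 1.57% at 112 and 3.11% at 224. Group values average these over the panels. The original schedule uses 364, 421 and 533 days (Days 365, 422 and 534 less 1).

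| Scenario, R = 5% | 10^7 | 10^4/10^5 | Pooled placebo | Placebo minus 10^7 |
|---|---|---|---|---|
| Original schedule | 5.00% | 7.24% | 5.82% | 0.82 points |
| Amendment 04 minimum, all doses given | 0.79% | 3.11% | 1.64% | 0.85 points |
| Amendment 04 minimum, no Day 169 doses | 0.79% | 0.79% | 0.97% | 0.18 points |

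With R = 20% and all doses given, the risks are 3.4% (10^7), 12.8% (10^4/10^5) and 6.9% (pooled placebo). Without Day 169 doses they are 3.4%, 3.4% and 4.1%.

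**5. Reading the table.** The ratio of placebo to 10^7 is 5.82/5.00 = 1.16 originally, 1.636/0.786 = 2.08 at the minimum with all doses, and 0.966/0.786 = 1.23 without Day 169 doses. On the difference scale used in Section 9.6.1, the distortion in the all-doses case is about the same as before the amendment. These rows use the minimum for everyone. Because no maximum is set, actual follow-up may depart from them.

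**The case against.** The strongest defence is the randomization. V591 against placebo is the primary objective, and 4:1 allocation within every panel gives both arms the same expected follow-up, within a panel and with all panels pooled. The 10^5 and 10^6 doses have matching panels (A/B, C/D, G/H, I/J, K/L), so recruitment order favours neither. Section 9.6.1 calls the Tier 2 intervals descriptive. In a group of 20, one participant is 5 percentage points, so a distortion below 1 point is small beside sampling error. All of this stands. It confines the problem to dose-level contrasts and limits its weight, but supplies no cut-off for those contrasts.

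Several stronger readings are tempting and are not supported:
- *Section 4.3 cuts off events at the sponsor's decision.* It does say "the study end will be defined as the date of the Sponsor decision, and this end of study date supersedes the definitions outlined above", but only for a decision that follows a pause and review, and it defines study end. Collection is governed by Section 8.4.1, so a loss of primary-endpoint events cannot be inferred.
- *Section 8.11.4 contradicts itself on 365 days.* The sentence "a subsequent follow-up telephone call should be made at 365 days or after" belongs to a paragraph on participants who discontinue, whereas the Amendment 04 paragraph covers everyone. The firmer leftovers are the Synopsis and Section 6.6.
- *A stated 12-month safety objective is lost.* Twelve months is a follow-up length; no objective names it.
- *The amendment created the unequal follow-up.* Section 8.3 already had last visits at Day 365, 422 or 534. The amendment removed the fixed end.
- *The second-dose text conflicts with the endpoint definition.* Section 8.11.2 still says Day 57 and Day 169 participants "will receive the second intramuscular injection of V591 or placebo into the deltoid muscle", and Section 8.11.4 does not address pending doses. That is a gap to reconcile, not a demonstrated conflict over the endpoint.

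**Conclusion.** The concern holds for dose-level comparisons. The SAE and MAAE endpoints now have a floor of 56 days after the last vaccination, no ceiling and no common cut-off. Twelve-month wording remains in two places, active and spontaneous reports can mix, and the SAP's proportions ignore time at risk. A reader should not infer that the overall V591 against placebo comparison is biased by follow-up; the design protects it.

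The groups most exposed are 10^7 and 10^4/10^5, each confined to one panel of 20 V591 recipients. Under the stated assumptions (constant hazard, no vaccine effect, 5% risk over 364 days, minimum follow-up, placebo pooled), 10^7 shows 0.79% against 1.64% if all second doses are given, or 0.79% against 0.97% if Day 169 doses are not. The documents contain no final-visit dates, counts of second doses given or MAAE rate, so these figures show direction and order of size only.

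**What to change.** In the SAP, for the final analysis:
- For dose-level comparisons of SAE, MAAE and ECI, count events per injection, from vaccination through 56 days, closing the first window at dose 2 if that comes sooner. With Day 57 ± 3, dose 2 can fall on Day 54, which is 53 days after dose 1, so unclosed windows would overlap. Counting per injection also keeps two-dose participants from contributing about twice the time at risk. Section 9.6.1 already plans summaries after each dose for two-dose panels.
- Compare each dose group with placebo from the same panels, or stratify by panel, and state which.
- Keep the full-duration V591 against placebo summary, stratified by panel or with exposure-adjusted rates.
- List spontaneous reports received after the final visit separately.
- Limit the comparative safety claim to the follow-up completed.

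In the protocol, reconcile the Synopsis, Section 6.6 and Section 4.3 with Section 8.11.4 on when follow-up ends. Also reconcile Section 7.1 (scheduled visits continue if dose 2 is missed), Section 8.1.8.1 and Section 8.11.2 with Section 8.11.4 for participants who have not had dose 2. Which clinical rule applies is for the sponsor to decide.

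The cost is wording and some added tables, with no new data. The price is precision: a full Part 2 panel has 5 placebo recipients, so panel-matched intervals will be wide, and events after 56 days leave the dose-level table, although they stay in the full-duration summary if they were collected by the final visit.
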